symptoms, anxiety symptoms, and withdrawal symptoms during TBS treatment. Evaluate the level of continued use of methamphetamine during TBS treatment.

This pilot study will focus on our ability to engage patients with methamphetamine use disorder in TBS treatment and to complete a series of assessments over three months. We expect to observe reductions in cravings, withdrawal and related symptoms over time, and changes in anterior cingulate cortex functional connectivity from baseline to 4 weeks. Differences between subjects randomized to receive stimulation at the DLPFC and MPFC will be examined.

Significance

Methamphetamine (MA) use can cause many serious adverse health consequences and is of particular concern in Iowa. In the 2017 Treatment Episode Data Set (TEDS), 27.7% of substance use disorder treatment admissions involved MA as the primary substance, representing 7,641 admissions, second only to alcohol. Overdose deaths in Iowa involving MA roughly doubled to 91 from 2013 to 2018.(1,2) Treatment for MA use disorder (MAUD) is primarily psychosocial, rates of treatment induction and retention are poor, and relapse rates are high.(3) There is a pressing need to identify effective interventions that enhance psychosocial treatments. rTMS is a non-invasive brain stimulation technique that effectively treats major depressive disorder and is considered safe, well-tolerated, and potent. rTMS has increasingly been studied to treat addiction.(4-7) The dorsolateral prefrontal cortex (DLPFC), a brain region implicated in regulatory processes related to emotion, motivation, and craving, is a common target for rTMS. DLPFC stimulation using high frequency rTMS has reduced craving in many studies of addictive disorders, including cocaine and MA use disorders.(4) Despite these encouraging findings, no trials have reported on the efficacy for reducing MA use or preventing relapse. iTBS is a type of TMS has been studied in depression and shown to have equivalent efficacy to rTMS, and treatments can be delivered much more quickly than traditional rTMS.(8) In contrast to high-frequency rTMS and intermittent theta burst stimulation, which increase neuronal excitability, continuous theta burst stimulation (cTBS) decreases excitability. cTBS targeting the MPFC during drug cue activation reduced craving and related brain

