TMS treatment using theta burst stimulation will be provided 5 days in the first week, five days in the second week, and three times per week in weeks 3 and 4. The start day will be somewhat flexible. Subjects will participate in 5 treatment sessions in each of the first two 7-day periods, and three treatment sessions in each of the third and fourth 7-day periods (treatment weeks). Theta burst stimulation can be completed in as little as 3 minutes per treatment (two sites), so these visits should take roughly 15-20 minutes total when once-weekly additional assessments are not being completed. We will measure blood pressure and pulse prior to each treatment. If systolic blood pressure exceeds 160 mmHg, diastolic blood pressure exceeds 100 mmHg, or pulse exceeds 110 beats per minute, then we will confirm this with a second measurement. If it is confirmed by a second measurement, then the treatment will be withheld, and a clinician contacted to assess the patient. Before each treatment, we will also ask the subject when they last used methamphetamine. Treatment may be withheld if it is too recent to minimize risk of adverse effects, particularly seizure. Participants will be asked to report craving using a single question before and after each treatment. Participants will only be asked to report any adverse event experiences at these visits.

On the last day of TMS in each treatment week when TMS is administered, the subject will be asked to complete additional assessments. At 1 week, 2 weeks, and 3 weeks, these will involve completion of surveys. At weeks 1 and 3 only the Brief Substance Craving Scale will be administered, while additional survey instruments will be administered after week 2. These visits will also involve reporting of the number of days in the last week in which they used methamphetamine as well as whether they remain engaged in a psychosocial treatment and what treatments (partial hospitalization, intensive outpatient, outpatient medical, outpatient psychotherapy, group therapy, other, none). If they were engaged in partial hospitalization or intensive outpatient treatment, we will ask whether they completed the planned course of treatment or stopped early.

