After the last treatment in week 4, the subject will be asked to again complete all assessment instruments, provide information on substance use in the last week, complete the psychological tests, submit a urine drug screen (if there is not a recent result on file in their EHR), and complete fMRI imaging. If the subject elects

to participate in the optional EEG and timing task, this will add about an hour to this visit. If they elect to participate in this optional EEG and task, we will be adhering electroencephalogram (EEG) leads to their scalp and then have them perform 2 blocks of the interval timing task where they estimate the passage of a specified (3 or 12 second) passage of time (~22min - 11 min blocks). The beginning of the trial is indicated by the presentation of either a 3 or a 12 on the computer screen which also indicates the duration of time the subject should estimate. During performance, we will collect electroencephalographic data from patients which will be analyzed offline.

TMS treatment will end at this time. We will then plan follow-up visits at 8 weeks and 12 weeks after the start of treatment, which can be completed by phone/online or in person base on the subject's preference. At these visits subjects will complete the survey-based assessments. They will also be asked about the number of days of methamphetamine use in the last week and their current psychosocial treatment modality.

An example study schedule and full list of assessments I provided below.

Figure 1: Example Study Schedule

Study Week	Monday	Tuesday	Wednesday	Thursday	Friday
1	First visit: determine eligibility to continue, questionnaires, psychological testing, urine drug screen if needed, MRI, optional EEG (3-5 hours)				
1	TMS	TMS	TMS	TMS	TMS, questionnaires, urine sample if needed (about 30 minutes)
2	TMS	TMS	TMS	TMS	TMS, questionnaires, urine sample if needed (45-60 minutes)
3	TMS		TMS		TMS, questionnaires, urine sample if needed (about 30 minutes)
4	TMS		TMS		TMS, questionnaires psychological testing, urine sample if needed, MRI, optional EEG (3-5 hours)
8	One follow-up visit or phone call to complete questionnaires (45-60 minutes)				
12	One follow-up visit or phone call to complete questionnaires (45-60 minutes)				

Figure 2: Schedule of study assessments by visit

Measure	Time to complete (minutes)	First Visit	Last TMS day week 1	Last TMS day week 2	Last TMS day week 3	Last TMS day week 4	Week 8	Week 12

Interview Questions								

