TMS will be administered by combining an FDA-approved protocol and a protocol that has been previously studied with no notable differences in adverse effects, and will be overseen by a psychiatrist in the clinical TMS service in the standard fashion.

We will measure blood pressure and pulse prior to each treatment. If systolic blood pressure exceeds 160 mmHg, diastolic blood pressure exceeds 100 mmHg, or pulse exceeds 110 beats per minute, then we will confirm this with a second measurement. If it is confirmed by a second measurement then the treatment will be withheld and a clinician contacted to assess the subject and their potential need for acute medical care. We will also ask the person when they last used methamphetamine, and withhold treatment if we believe they may still be intoxicated with methamphetamine.

Minimizing the risks of MRI:

To reduce the risk of a metal object flying through the air and hitting the subject, technologist or nearby person, we require that all people involved with the study remove all metal from their clothing, pockets and body prior to entering the scan room. No metal objects will be brought into the magnet room while the subject is inside the room. In addition, the door to the room remains closed throughout the entire study so that no one accidentally takes a ferrous metal object into the scan room. We also have a ferromagnetic detector for the research suite. The metal detector will work in tandem with our MRI screening sheet to ensure no metal is accidentally overlooked and taken into the scan room.

-Subjects will be given either ear plugs or headphones to reduce the risk of hearing damage.

-In the event that an abnormal finding is suspected, a radiologist trained in reading the examination will be consulted. If it is felt that the subject needs to be notified in order to seek out further medical advice, a physician will then contact the subject to discuss the issue.

-Exposure to magnetic fields and radiofrequency fields will be kept to a minimum by setting a cutoff time of any study of 90 minutes in the magnet.

-Subjects will be given a squeeze ball while in the MRI scanner to alert the investigators to stop the study.

Minimizing emotional risks:

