This is a pilot study without an untreated control group so will not be able to establish that the treatment is causal in improving outcomes. The overarching goal is to evaluate the ability to recruit and retain subjects, establish safety of the intervention in this population, evaluate target engagement of TMS using fMRI, and to determine the extent to which patient symptoms and substance use appear to improve during participation in treatment. We anticipate approximately 20 subjects, which should be adequate to statistically detect clinically meaningful changes in symptoms and other outcome measures, depending on attrition. We will randomize order of treatments to gather preliminary data on any differences, but do not anticipate power to detect significant differences in effect by order of treatment with this sample size.

Outcomes

Primary outcomes:

1. Retention in the Study: Measured from Baseline to 12 weeks
2. Retention in Psychosocial Treatment: Measured from Baseline to 18 days (self-reported)

Secondary outcomes (used all available data points as specified in figure 2):

1. Functional Connectivity of the Dorsolateral Prefrontal Cortex and Anterior Insula—change from baseline to 4 weeks. Measured by correlation of region activity over MRI time series data, averaged for left and right hemisphere.
2. Functional Connectivity Dorsolateral Prefrontal Cortex and Anterior Cingulate Cortex—change from baseline to 4 weeks. Measured by correlation of region activity over MRI time series data, averaged for left and right hemisphere.
3. Functional Connectivity of the Medial Prefrontal Cortex and Ventral Striatum—change from baseline to 4 weeks. Measured by correlation of region activity over MRI time series data, averaged for left and right hemisphere.
4. Kirby Delay Discounting Questionnaire, 27 Item

5. Number of Days of Methamphetamine Use in the Past Week
6. Urine Drug Screen Positive for Stimulant
7. Brief Substance Craving Scale
8. Brief Addiction Monitor—Use Subscale
9. Brief Addiction Monitor—Risk Factors Subscale
10. Brief Addiction Monitor—Protective Factors Subscale
11. Brief Addiction Monitor—Satisfaction with Progress Toward Achieving Recovery Goals (question 17)
12. Quality of Life Enjoyment and Satisfaction Questionnaire—Short Form
13. Patient Health Questionnaire--8 Item Scale
14. Generalized Anxiety Disorder 7-item Scale
15. Assessment of Recovery Capital
16. Positive and Negative Affect Scale—Positive Affect Score

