17. Positive and Negative Affect Scale—Negative Affect Score
18. Pittsburgh Sleep Quality Index
19. Difficulties in Emotion Regulation Scale--Short Form
20. UPPS-P Impulsive Behavior Scale, 59-item Revised Version

Safety outcomes

Adverse events are reported at each TMS treatment visit, or if otherwise volunteered by subject.

Populations to be analyzed

Intention to treat: Subjects will be analyzed in the groups they were randomized to. However, only complete data will be used, and subjects were discontinued from the study if they missed more than 4 TMS treatments.

Analyses

Descriptive statistics will be examined for demographic and other variables, overall and by intervention group.

For other analyses, a fixed time will be assigned for each study visit, which approximates the time at which the visit would have occurred on a typical study schedule.

Primary outcomes

The primary analysis will compare intervention groups (DLPFC first or MPFC first) on time to discontinuation in the study and time to discontinuation of psychosocial treatment. The latter is defined as a participant indicating they are no longer in or seeking treatment. All subjects were in treatment or planning treatment at baseline, as an inclusion criterion. Time retained in the study or treatment will be described using Kaplan-Meier curves, and intervention groups will be compared using log-rank tests.

Secondary outcomes

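### Admitting recent methamphetamine use can cost a TMS session, so self-reported days of use in weeks 1–3 carry an incentive to under-report that the SAP neither checks against urine nor separates from the 12-week slope

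*Combined protocol and SAP*

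**What the plan says.** Study Procedures sets the pre-session check: "Before each treatment, we will also ask the subject when they last used methamphetamine". The consequence follows: "Treatment may be withheld if it is too recent to minimize risk of adverse effects, particularly seizure". The section on minimizing the risks of TMS words the rule differently: "withhold treatment if we believe they may still be intoxicated with methamphetamine". Neither gives a time limit.

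Of the assessments on the last TMS day of weeks 1–3, Study Procedures says: "These visits will also involve reporting of the number of days in the last week in which they used methamphetamine". Whether this comes before or after that day's session is not stated. Week 4 is different: "After the last treatment in week 4, the subject will be asked to again complete all assessment instruments". Figure 2 places the use report among the interview questions, at baseline, weeks 1–4, week 8 and week 12.

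The SAP lists secondary outcome 5 as "Number of Days of Methamphetamine Use in the Past Week". The related secondary objective is: "Evaluate the level of continued use of methamphetamine during TBS treatment". Figure 2 schedules urine screens at baseline and weeks 1–4 only, and only if needed. The text for baseline and week 4 lets a recent health-record result stand in. The SAP models urine positivity as an outcome of its own and nowhere compares it with self-report.

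Under populations to be analyzed, the SAP adds: "subjects were discontinued from the study if they missed more than 4 TMS treatments". It does not say whether a withheld session counts as missed.

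**The concern.** The same person, on the same day, answers a question that can cost a session and a research question about the past seven days. Someone who has just denied recent use has reason to keep the second answer consistent with the first. At weeks 8 and 12 treatment is over. At baseline active use disorder is an entry criterion and normally no session is pending, although Study Procedures allows TMS to start on the day of the first visit.

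A change in reporting that starts with treatment would be hard to tell from a change in use, because there is no untreated control group. The SAP concedes that the study cannot show that treatment caused improvement. That caveat concerns why use fell, whereas this point concerns whether it fell. What is at stake is the objective on use during treatment. The section on potential benefits also names improvement in substance use, alongside feasibility, symptoms and connectivity, as grounds for a randomized trial.

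**Working it through.** The plan gives no figure to reproduce here. The sample size of about 20 comes without an effect size, standard deviation, alpha or power, and no expected level of use is given. The check is therefore about direction and relative size.

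**Inputs from the documents.** Visit times from Figure 2, with baseline as 0: weeks 0, 1, 2, 3, 4, 8 and 12. The SAP plans a linear mixed model in continuous time, using all scheduled points.

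**Assumptions, not in the documents.** No true change; honest reports at baseline and weeks 8 and 12; an under-report b(t) = −1 day either in weeks 1–4, or in weeks 1–3 only with an honest week 4.

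**Formula.** Slope bias = Σ(t − t̄)·b(t) / Σ(t − t̄)². With complete data and a random intercept, the mixed-model slope has the same bias.

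**Weeks 0–12.** t̄ = 30/7 = 4.286; Σ(t − t̄)² = 238 − 900/7 = 109.43.
- Under-reporting in weeks 1–4: numerator −(10 − 4 × 4.286) = 7.143; bias 7.143/109.43 = +0.065 day/week.
- Under-reporting in weeks 1–3: numerator −(6 − 3 × 4.286) = 6.857; bias 6.857/109.43 = +0.063 day/week.

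**Weeks 0–4.** t̄ = 2; Σ(t − t̄)² = 10.
- Under-reporting in weeks 1–4: −(10 − 8)/10 = −0.20 day/week, or −0.8 day over four weeks.
- Under-reporting in weeks 1–3: −(6 − 6)/10 = 0.

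| Under-report of 1 day in | Mean of weeks 1–4 minus baseline | Week 4 minus baseline | Slope, weeks 0–4 | Slope, weeks 0–12 |
|---|---|---|---|---|
| Weeks 1–4 | −1.0 | −1.0 | −0.20 | +0.065 |
| Weeks 1–3 | −0.75 | 0 | 0 | +0.063 |

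All entries scale with the under-report. Half a day halves them and two days doubles them, so the first row's slopes run from −0.10 to −0.40 over weeks 0–4 and from about +0.03 to +0.13 over weeks 0–12.

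**Dropout.** Suppose only a share of participants gives reports after week 4. With a random intercept and an intraclass correlation of 0.5, under-reporting in weeks 1–4 biases the overall slope by about +0.044 if 50% continue, +0.01 if 25% do and −0.05 if 10% do. Correlations of 0.3 to 0.7 move these by at most 0.003. With under-reporting in weeks 1–3 only, the values are about +0.058, +0.050 and +0.035. The sign of the planned slope's bias thus depends on follow-up and on whether week 4 is affected.

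**The case against.** The strongest reply is that the planned analysis would not show a false fall. Outcome 5 has seven time points, and the SAP keeps change-from-baseline tests as a fallback for outcomes measured twice. With honest reports at weeks 8 and 12, the fitted slope tilts upward. This stands. A reader might infer that the plan is set to produce a spurious significant reduction in use; the documents do not support that. The false fall belongs to treatment-period values against baseline, which is still what the objective on use during treatment asks about.

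A reader might also infer that all four treatment weeks are equally exposed, or that admitting use leads towards removal from the study. Neither is established. The week 4 report follows the last session, and the documents do not say that withheld sessions count as missed.

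It is also fair that the rule concerns recent use or intoxication while the outcome covers seven days, so admitting use several days earlier need not cost anything. The link between the two answers is consistency, which is plausible but not demonstrated.

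Urine is an imperfect check. The SAP outcome is positivity for stimulants, not methamphetamine, although excluding people under medical treatment with stimulants limits that problem. With no screens at weeks 8 and 12, reporting on and off treatment cannot be compared.

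Finally, both order groups face the same rule, so the group-by-time test is not expected to be biased, and the primary outcomes concern retention. This stands and limits the consequence.

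**Conclusion.** The point holds as a risk to one secondary outcome. The incentive to under-report is direct in weeks 1–3, indirect at week 4, usually absent at baseline and absent at weeks 8 and 12. Whether participants act on it cannot be known from the documents.

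Per day under-reported, the treatment-period mean would sit 0.75 to 1.0 day too low against baseline. The slope over weeks 0–4 would be biased by 0 to −0.20 day/week, depending on week 4, and the SAP's 12-week slope by about +0.06 day/week with complete data. These sizes rest on an assumed constant under-report, no true change and honest reports at the other visits. One linear slope through all seven visits can therefore hide a distortion that a plain before-and-during comparison would show as benefit.

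**What to change.** 1. In the SAP's secondary analyses, add a sensitivity analysis of outcome 5 in which zero reported days with a stimulant-positive urine screen taken at the same visit counts as at least one day. Report the number of such discordant visits, out of visits with a same-visit screen, at baseline and at each of weeks 1–4. If all of about 20 participants report, each visit recoded to one day raises that visit's mean by 1/20 = 0.05 day.
2. Summarise outcome 5 by visit, or model visit as a category, so that the treatment-period level against baseline is shown apart from the 12-week slope.
3. Optionally, in weeks 1–3 collect the past-week report as a self-completed REDCap form after that day's session. This reduces the incentive without removing it, since the pre-session answer has already been given.

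Leave the safety question and the withholding rule unchanged, and add no promise about how answers affect treatment. The sponsor must reconcile the two wordings of that rule and state whether withheld sessions count as missed.

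The first two changes use data already planned; the third changes the order and mode of one two-minute item at three visits. The use estimate may become slightly less favourable. The urine check is only partial: screens are conditional, can be replaced by a health-record result and are not specific to methamphetamine, and the recoding catches only reports of zero. A discordant visit is a flag, not proof of a false denial.

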Screening questions that warrant follow up if the participant answers "yes":

- Have you been diagnosed with a methamphetamine use disorder? (follow up- providers to determine if participant should have a methamphetamine use diagnosis, if not currently diagnosed)
- Are you claustrophobic or afraid of small, closed-in spaces? (follow-up- participant needs to confirm that they can handle being in an MRI machine through additional questions)
- Do you have a problem with loud noises? (follow-up- participant needs to confirm that the noises from the MRI are not too loud through additional questions)
- Have you ever had a neurosurgical procedure? (follow up- type of procedure matters)
- Have you been diagnosed with another neurological disorder? (follow-up- type of disorder matters)
- Are you able to make it to all visits for this study without assistance?
Additional information: This involves a baseline visit, then visits five days a week for two weeks and three days a week for two more weeks. The visits need to take place Monday through Friday, but we can start most any day depending on what's convenient for you. There will also be follow-up visits that can be completed by phone or in person one month and two months after the other visits are completed.
 - If not, Please explain any additional services you may need to get to and from study appointments, (i.e. transportation)

Randomization

The randomization scheme was block randomization stratified by study site, with block sizes of 4 and a 1:1 ratio, designed to ensure approximate balance in the number of subjects. Subjects are randomized to receive stimulation at the DLPFC or MPFC first, although both groups receive stimulation at both sites at each visit. The subject is assigned to a group at the first TMS treatment visit.

Intervention

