Most secondary outcomes will be examined using linear mixed models. These allow for estimation of within group change over time as well as between group differences in change over time. Group by continuous time interaction terms will be the primary test of hypotheses for differences between groups. For outcomes measured at only two time points (baseline and week 4), if sample size is not adequate or mixed models do not converge, changes from baseline to the second measure will be calculated. Wilcoxon-rank sum tests or t-tests comparing differences in changes from baseline to week 4 will be used to compare groups, as appropriate based on the data distribution. A generalized estimating equations model clustered on subject with a logit link, with empirical standard error estimates, will be used to analyze the outcome of positive urine drug screens for stimulants, as this is binary, and this approach does not assume a correlation structure. The primary analysis of this outcome will still use a group by continuous time interaction to examine whether the odds of a positive urine drug screen decreases over time in each group, and whether any reduction over time differs between groups.

Missing data

As this is a pilot study with a small sample size, and dropout is expected, analyses will use all available data as feasible for randomized subjects who received at least one treatment, irrespective of the number of data points collected. For changes in functional connectivity as measured by MRI, only subjects with both baseline and 4-week assessments will be included. No imputation of data will be performed.

References

1. Governor's Office of Drug Control Policy. News Release - Iowa Drug Control Report: Life-Changing Progress Amid Evolving Threats.
<https://odcp.iowa.gov/news-release-iowa-drug-control-report-life-changing-progress-amid-evolving-threats>. Published 2019. Updated November 13, 2019. Accessed December 13, 2019, 2019.
2. Iowa Department of Public Health. Substance Abuse Brief, December 2018, Issue 7.
https://idph.iowa.gov/Portals/1/userfiles/133/IASubAbuseBriefNewsletterDec2018_Final.pdf. Published 2018. Accessed December 13, 2019, 2019.

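### The claim that about 20 subjects is adequate to detect meaningful change is unsupported, and no planned analysis pools change over the two treatment orders to match it

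*Combined protocol and SAP*

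**What the plan says.** SAP, Sample Size Justification: "We anticipate approximately 20 subjects", "which should be adequate to statistically detect clinically meaningful changes in symptoms and other outcome measures", with the rider "depending on attrition". The next sentence says that order is randomised for preliminary data and that power to show a difference by order is not expected. No alpha, power, effect size, standard deviation or attrition rate is given.

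Protocol, Randomization: allocation is stratified by site, "with block sizes of 4 and a 1:1 ratio". Protocol, Intervention: apart from the order of the two stimulation sites, treatment is the same in both groups.

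SAP, Analyses, Secondary outcomes: most outcomes go into linear mixed models. Of these the SAP says: "These allow for estimation of within group change over time as well as between group differences in change over time". The group-by-time term is the leading test of group differences. The GEE for the urine screen asks "whether the odds of a positive urine drug screen decreases over time in each group" and whether any reduction differs between groups. For outcomes measured only at baseline and week 4, if the sample is too small or the model fails to converge, changes are calculated and a rank-sum test or t-test compares the groups.

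SAP, Analyses: results for all subjects together are mentioned only for descriptive statistics. SAP, Missing data: "dropout is expected", with no rate given.

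**The concern.** The sample size is argued from change over time, but the analysis section is organised around the comparison of orders, for which the SAP itself disclaims power. Because everyone receives both stimulations at every visit, the order comparison says nothing about the effect of the combined treatment. Yet the protocol's Secondary Objectives ask for the effect size of the dual-target treatment on connectivity and impulsivity. Potential Benefits to Society says that improvements in symptoms, use and connectivity, together with feasibility, would justify a controlled trial.

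The estimate that bears on that decision is therefore either reported in two groups of about 10 or, in the fallback, not tested at all. If pooling is left open, it can also be chosen after the results have been seen.

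**Working it through.** **1. The plan's own figure.** The number 20 cannot be reproduced, because none of the inputs to a power calculation is stated. What can be computed is the change that a given number of subjects would detect.

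**2. Inputs.**
- Total about 20 (Sample Size Justification).
- 1:1 allocation (Randomization), so about 20 / 2 = 10 per order.
- Attrition is expected but has no rate. Assumed 30%: 20 × 0.7 = 14 completers, 7 per order.
- Assumed: 80% power, two-sided 5%.

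**3. Outcomes concerned.** By Figure 2 of the protocol, 6 of the 20 secondary outcomes have only two time points: three connectivity measures, delay discounting, emotion regulation and UPPS-P. The other 20 − 6 = 14 have 4 to 7 visits; one of these, the urine screen, is binary.

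**4. Detectable change, two time points.** Let d = mean change / SD of individual change. Power of the paired t-test is P(T > t crit), where T is noncentral t with n − 1 df and noncentrality d√n. Solving for 80% gives the t-test column. The check is the normal approximation (1.96 + 0.84)/√n.

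| Analysis | n | d (t-test) | Normal check |
|---|---|---|---|
| Pooled over order | 20 | 0.66 | 0.63 |
| Pooled, 30% attrition | 14 | 0.81 | 0.75 |
| One order group | 10 | 1.00 | 0.89 |
| One order group, 30% attrition | 7 | 1.27 | 1.06 |

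For example, at n = 10, d√n = 0.996 × 3.162 = 3.15; at n = 20, 0.660 × 4.472 = 2.95. If a joint model estimates error from both groups (18 df), the one-group figure is 0.94. The order comparison at 10 per group needs 1.32 SD.

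Power for a change of 0.5 SD of change is 29% at n = 10 and 56% at n = 20. For 0.8 it is 62% and 92%. Reaching 80% power for 0.5 would take 34 subjects.

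**5. Units.** These are SDs of individual change. In outcome SDs, multiply by √(2(1 − ρ)), where ρ is the correlation between the two measurements; the documents do not give it.

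| ρ | Factor | n = 10 | n = 20 |
|---|---|---|---|
| 0.3 | 1.18 | 1.18 | 0.78 |
| 0.5 | 1.00 | 1.00 | 0.66 |
| 0.7 | 0.77 | 0.77 | 0.51 |
| 0.8 | 0.63 | 0.63 | 0.42 |

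**6. Repeated continuous outcomes.** Under a random-intercept linear trend with complete data, the standard error of the slope is SD × √((1 − ρ)/(n Sxx)), where Sxx is the sum of squared deviations of the visit times. Detectable change over 12 weeks, in outcome SDs, for ρ = 0.5 to 0.7:

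| Visits | One order, n = 10 | Pooled, n = 20 |
|---|---|---|
| 4 | 0.94 to 0.73 | 0.63 to 0.49 |
| 5 | 0.88 to 0.68 | 0.58 to 0.45 |
| 7 | 0.81 to 0.63 | 0.54 to 0.41 |

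This model is optimistic because it omits random slopes.

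**7. Claim against analysis.** The justification concerns change over time. The models are described by group; the fallback tests groups only; no sentence names a test of change in all subjects.

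**The case against.** The strongest reply is that the SAP describes what mixed models can do and does not close the list of tests. The interaction is put first only for group differences, and a time effect averaged over order can be taken from the same model. The objectives are worded for all patients. This stands in part: a pooled estimate is not excluded. But it is not specified either, and the two-time-point fallback leaves the mixed model altogether and tests only the order difference.

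A reader might infer that the planned analyses can detect only changes of about 1 SD. The documents do not support that. The figure is in SDs of individual change and fits the six baseline/week-4 outcomes. The symptom scales are measured repeatedly and do better under the model in step 6, and no SD figure applies to the urine screen.

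A reader might also infer that the adequacy claim is false. That cannot be shown: meaningful change is not defined for any outcome, and the claim is conditional on attrition.

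Finally, this is a pilot with feasibility as its primary objective, and the SAP already says that it cannot establish causation and lacks power by order. That limits the weight of the point. It does not explain why the change estimate should be split by an order that is not expected to matter detectably.

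**Conclusion.** The point holds in this form: the adequacy statement has no stated basis, and the analysis section does not prespecify the pooled estimate of change that would correspond to it. For a paired two-time-point outcome, pooling over order lowers the detectable change from 1.00 to 0.66 SD of individual change with complete data, and from 1.27 to 0.81 with 30% attrition.

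These figures rest on assumed 80% power, two-sided 5% and an assumed attrition rate. Attrition can only worsen them, but by how much is unknown. The gain for repeated outcomes goes the same way, with sizes that depend on ρ and the model. The conclusion is that the claim is unsupported and unmatched, not that 20 subjects are too few or that a pooled analysis is ruled out. The primary feasibility objective is not affected.

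**What to change.** 1. In Analyses, Secondary outcomes, prespecify change over time averaged over the two orders, with a 95% CI, as the main secondary estimate. Do the same on the log-odds scale for the urine screen. Keep group-by-time as exploratory.
2. In the two-time-point fallback, add a one-sample t-test or signed-rank test of change in all subjects with both measurements, with its estimate and interval.
3. Replace the adequacy sentence with a conditional one, for example: *For a paired comparison at two time points, with 80% power and two-sided 5%, 20 completers detect a mean change of 0.66 SD of individual change and 14 completers (30% attrition, assumed) 0.81 SD, against 1.00 SD within one order group of 10. These figures do not apply to the repeatedly measured outcomes or to the urine screen.*
4. If the sponsor wishes to keep a claim about meaningful change, it must state that change for each key outcome.

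Adjustment for site is optional: with three sites and about 20 subjects it costs degrees of freedom and is not needed here.

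The cost is SAP wording and no extra subjects. The downside is that the stated precision becomes explicit and less favourable than the present sentence. If outcome data have already been examined, the pooled estimate should be labelled as added afterwards.
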